ECG 12 lead ^{c, d)}		X		X		X		X		X	X	X	X
Vital Signs ^{d)}		X		X		X		X		X	X	X	X
Blood Chemistry ^{d)}		X		X		X		X		X	X	X	X
Hematology ^{d)}		X		X		X		X		X	X	X	X
Urinalysis ^{d)}		X		X		X		X		X	X	X	X
Coagulation ^{d)}		X		X		X		X		X	X	X	X
Anti Drug Antibody ^{e)}		X				X					X		
Urine Injury Biomarkers ^{d)}		X		X		X		X		X	X	X	X
Blood Injury Biomarkers ^{d)}		X		X		X		X		X	X	X	X
Pregnancy Test								X			X	X	X
Blood PK Sample [REDACTED]	2	2	2	2	2	2	2	X		X	X	X	X
Blood PK Sample [REDACTED]		2		2		2		X		X	X	X	X
Blood PK Sample [REDACTED]				2				X		X	X	X	X
Urine PK Sample				2									
NUC PK									X				
HBV DNA quant ^{d)}		X		X		X		X	X	X	X	X	X
HBV serology ^{d,g)}		X		X		X		X		X	X	X	X
HBV RNA quant ^{d)}		X		X		X		X		X	X	X	X
HBV core related antigen ^{d)}		X		X		X		X		X	X	X	X
HBV DNA Genotyping (Rebound)									X				
Adverse Events	X	X	X	X	X	X	X	X		X	X	X	X
Previous and Concomitant Treatments	X	X	X	X	X	X	X	X		X	X	X	X

Table 5 Schedule of Assessments – Main Table, Part 2b (CHB [REDACTED]) 12 weeks – as of Week 6) (cont.)

- a) For the assessments of Weeks 1 to 5, see the Part 2a/ Part 2b (CHB, 5 Week) Main SoA table. All visits can be done ± 3 days with the exception of the safety and follow-up visits on D134 and 182 (± 7 days).

At home nurse visits: vital signs, AEs and previous and concurrent treatments will be assessed; Blood for PK and other laboratory specimen may be collected as specified in the SoA table. ECG may be performed if appropriate. If site is not participating in home nurse visits, this will be an outpatient visit in clinic.

- b) Complete physical examination is required. At all other visits (or as clinically indicated), limited, symptom-directed physical examinations should be performed at the discretion of the Investigator.
- c) Twelve-lead ECGs will be obtained in triplicate (three consecutive interpretable 12-lead ECGs in less than 5 minutes) after the participant has been in a supine position for at least 10 minutes.
- d) Pre-dose (on days of study treatment administration).
- e) ADA samples to be taken pre-dose (when applicable).

- [REDACTED]
- g) HBV serology will include HBsAg (quantitative), anti-HBs (quantitative), HBeAg (qualitative) and anti-HBeAb (qualitative).
- [REDACTED]

- i) In case of HBV DNA rebound an unscheduled confirmatory HBV DNA quantification sample should be taken, a sample for HBV DNA genotyping and a sample for NUC PK.

**Table 6 Schedule of Assessments – Detailed Table, (CHB [REDACTED]

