4.1.3 Stopping Rules Criteria

Liver-related

Isolated elevations in liver transaminases (ALT or AST) in the absence of liver function abnormalities may occur after administration of RO7239958 as a recognized LNA SSO class effect. In addition to the LNA SSO class effect, CHB patients may also hypothetically experience transaminase flares if HBsAg suppression leads to immune-restoration. Stopping criteria have been developed to take these potential effects into account.

Part 1: If, at a given dose level, one or more of the criteria described below is fulfilled, dose-escalation to the next cohort will be paused in order to assess the possible underlying causes and relation to RO7239958. If a relation to study treatment cannot be excluded by the Investigator and the Sponsor's Medical Monitor, dose escalation will be halted.

Criteria:

- At least two of eight healthy participants receiving RO7239958 experience dose-limiting AEs (DLAEs) of an ALT or AST increase $> 5x$ the upper limit of normal (ULN; confirmed by retesting within 48 hours) with preserved measures of liver function (total bilirubin, and INR or prothrombin time [PT]),

or

- At least one of eight healthy participants receiving RO7239958 experiences one of the following DLAEs: confirmed (within 48 hours) increase in ALT or AST $> 3x$ ULN accompanied by confirmed total bilirubin $> 2x$ ULN, INR > 1.5 , or PT $\geq 1.5x$ ULN, or appearance of jaundice or symptoms suggestive of drug-induced liver injury (e.g., fatigue, nausea, vomiting, right upper quadrant abdominal pain or tenderness, fever, rash, and eosinophilia).

Part 2: If, at a given dose level and/or regimen, one or more of the criteria described below is fulfilled, dosing in a patient and in a given arm, and any dose escalation, will be paused in order to assess the possible underlying causes and relation to RO7239958. If a relation to study treatment cannot be excluded by the Investigator and Sponsor's Medical Monitor, dosing and any potential dose escalation will be halted.

Criteria:

- At least two of six patients receiving RO7239958 experience a DLAE of an ALT or AST increase of > 8-fold relative to the baseline value (defined as the average values of the two measurements taken within the screening period), confirmed by retesting within 48 hours, with preserved measures of liver function (total bilirubin and INR or PT),
or

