- At least one of six patients receiving RO7239958 experiences one of the following DLAEs: confirmed (within 48 hours) increase in ALT or AST > 3-fold the baseline value, accompanied by confirmed total bilirubin > 2x ULN, INR > 1.5, or PT \geq 1.5x ULN, or appearance of jaundice or symptoms suggestive of drug-induced liver injury (e.g., fatigue, nausea, vomiting, right upper quadrant abdominal pain or tenderness, fever, rash, and eosinophilia).

Repeat dosing of a participant within an arm will be delayed if the participant receiving RO7239958 experiences an ALT or AST increase > 5-fold and \leq 8-fold relative to the baseline value, confirmed by retesting within 48 hours, with preserved measures of liver function (total bilirubin and INR or PT). Dosing may resume when the ALT or AST levels return to \leq 5-fold the baseline value.

Other stopping criteria

All Parts: Dosing and dose-escalation in healthy participants in Part 1 and dosing for a patient and a treatment arm and any potential dose escalation in Part 2 will not be implemented as planned if one of the criteria described below is fulfilled, unless it is apparent to the Investigator and the Sponsor that the occurrence is not related to RO7239958.

Criteria: At least two of eight healthy participants or at least two of six CHB patients receiving RO7239958 experience one or more of the following DLAEs:

- Confirmed decline in eGFR < 60 ml/min
- Grade 3 or 4, or otherwise significant (as defined by the Investigator) RO7239958-related AEs of the same character, or Grade 3 or 4 laboratory abnormalities.
- Other findings (regardless of the incidence rates) that at the joint discretion of the Sponsor and the Investigator indicate that dosing and any dose escalation should be halted (see Section 7.1).

General considerations

Part 1: In case dose-escalation is stopped, lower doses within the tolerated dose-range could be investigated or a previous dose could be repeated in subsequent cohorts, by mutual agreement between the Sponsor and Investigator, in order to increase the amount of data within the tolerated dose-range.

Part 2: In case an arm is stopped, alternative regimens within a previously tolerated dose/exposure range could be further investigated, or a previous regimen could be repeated in subsequent arms, by mutual agreement between the Sponsor and Investigator, in order to increase the amount of data within the tolerated dose/exposure range.

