8.2.4 Clinical Safety Laboratory Assessments

Normal ranges for the study laboratory parameters must be supplied to the Sponsor before the study starts. A list of clinical laboratory tests to be performed is provided in [Appendix 4](#) and these assessments must be conducted in accordance with the separate laboratory manual and the SoA (Section 1.3).

The Investigator must review the laboratory report, document this review, and record any clinically relevant changes occurring during the study in the AE section of the CRF. The laboratory reports must be filed with the source documents. Clinically significant abnormal laboratory findings are those which are not associated with the underlying disease, unless judged by the Investigator to be more severe than expected for the participant's condition.

- In the event of unexplained abnormal clinically significant laboratory test values, the tests should be repeated immediately and followed up until they have returned to the normal range and/or an adequate explanation of the abnormality is found.
- If such values do not return to normal/baseline within a period of time judged reasonable by the Investigator, the etiology should be identified and the Sponsor notified.
- If laboratory values from non-protocol specified laboratory assessments performed at the local laboratory require a change in participant management or are considered clinically significant by the Investigator (e.g., SAE or AE or dose-modification) the results must be recorded in the CRF.

Results of clinical laboratory testing will be recorded in the eCRF or be received as electronically produced laboratory reports submitted directly from the central laboratory.

Additional blood or urine samples may be taken at the discretion of the Investigator if the results of any test fall outside the reference ranges, or clinical symptoms necessitate additional testing to monitor participant safety.

Where the clinical significance of abnormal lab results is considered uncertain, screening lab tests may be repeated before randomization to confirm eligibility.

If there is an alternative explanation for a positive urine or blood test for drugs of abuse, e.g., previous occasional intake of a medication or food containing for example, codeine, benzodiazepines or opiates, the test could be repeated to confirm washout.

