Appendix 4 Clinical Laboratory Tests

The tests detailed in [Table 1](#) will be performed locally for Part 1 of the study and by the central laboratory for Part 2 (with the exception of urinalysis specific gravity, urine dipstick, and alcohol testing which will be performed locally).

In Part 2, local laboratory results are only required in the event that the central laboratory results are not available in time for either study treatment administration and/or response evaluation. If a local sample is required, it is important that the sample for central analysis is obtained at the same time. Additionally, if the local laboratory results are used to make either a study treatment decision or response evaluation, the results must be captured in source documentation and entered as a comment into the eCRF.

Protocol-specific requirements for inclusion or exclusion of participants are detailed in Sections [5.1](#) and [5.2](#), respectively, of the protocol.

Additional tests may be performed at any time during the study as determined necessary by the Investigator or required by local regulations.

Table 1 Protocol-Required Safety Laboratory Assessments

Laboratory Assessments	Parameters
Hematology	
 Leucocytes, erythrocytes, hemoglobin, hematocrit, platelets, differential count (neutrophils, eosinophils, basophils, monocytes, lymphocytes, other cells).
Clinical Chemistry	
 Sodium, potassium, chloride, bicarbonate, glucose, urea, creatinine, cystatin C (and estimated creatinine- and cystatin C-based eGFR by CKD-epi equation [see Appendix 6]) total protein, albumin, phosphate, calcium, total and direct bilirubin, gamma-glutamyl transferase (GGT), alkaline phosphatase, ALT, AST, urate. In Part 2, Creatinine Kinase (CK) will be performed as reflex testing on any AST value $\geq 2 \times$ ULN. 
For additional assessments relating to exploratory safety BMs, please see Section 8.6.1.

Coagulation	
 INR, aPTT/ PT.
Viral Serology (Part 1)	
 HIV (HIV-1 antibody, HIV-1/2 antibody, HIV-2 antibody), Hepatitis B surface antigen (HBsAg), total hepatitis B core antibody (anti-HBc), hepatitis C virus (HCV) antibody.
Viral Serology (Part 2)	
 HIV (HIV-1 antibody, HIV-1/2 antibody, HIV-2 antibody), hepatitis C virus (HCV) antibody.

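### If Part 2b opens with a weekly arm, Table 5 schedules no chemistry or coagulation at 4 of the 7 doses after Week 5, so the liver rules in Section 4.1.3 are applied there on values drawn before the preceding dose

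*Combined protocol and SAP*

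**What the plan says.** **The rules.** For Part 2, Section 4.1.3 has a patient-level rule: "Repeat dosing of a participant within an arm will be delayed if the participant receiving RO7239958 experiences an ALT or AST increase" of more than 5-fold and at most 8-fold baseline, confirmed by retest within 48 hours, with bilirubin and INR or PT preserved. The resume step is "Dosing may resume when the ALT or AST levels return to" 5-fold baseline or less. The same section pauses dosing in the patient and the arm if two of six active patients exceed 8-fold. It does the same if one of six exceeds 3-fold with raised bilirubin, INR or PT, or with jaundice or suggestive symptoms. It says that isolated transaminase rises "may occur after administration of RO7239958 as a recognized LNA SSO class effect".

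**The schedule.** Table 3 governs Weeks 1 to 5 and marks chemistry and coagulation at each weekly dosing visit. Table 5 governs Part 2b from Week 6. It marks both on Days 43, 57 and 71, at discontinuation and at the four follow-up visits. Both are blank on Days 36, 50, 64 and 78. Footnote d makes these draws pre-dose on dosing days.

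**Laboratory handling.** Appendix 4 makes the central laboratory the default in Part 2. It requires local results only if "the central laboratory results are not available in time for either study treatment administration and/or response evaluation". Section 8.2.4 says of unexplained, clinically significant abnormal values that "the tests should be repeated immediately and followed up until they have returned to the normal range" or explained.

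**The concern.** The chemistry days after Week 5 coincide exactly with the dosing days of a two-weekly regimen. Tables 5 and 6 also carry PK columns that look like a weekly regimen, and for that regimen every second dose falls on a visit with no liver test. The most frequently dosed patients would therefore be the only ones who receive doses without a same-visit ALT.

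This is a first-in-human study of a drug whose class is expected to raise transaminases without symptoms. Twelve weeks of weekly dosing would be its longest and most intensive exposure. The delay rule and both liver stopping rules draw on the same samples. A silent rise that begins just after a scheduled check could be followed by a further dose before the next check finds it.

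**Working it through.** **Inputs**

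- Visits in Weeks 6 to 12 (Table 5): Days 36, 43, 50, 57, 64, 71, 78.
- Chemistry and coagulation in those weeks (Table 5): Days 43, 57, 71.
- Chemistry in Weeks 1 to 5 (Table 3): Days 1, 2, 8, 15, 22, 29.
- Dosing days by regimen. The labels are redacted, so these are inferred from paired pre-dose and 2-hour PK samples in Tables 5 and 6. The first column has the pair on all seven days, the second on Days 43, 57 and 71, and the third on Day 57 only. Table 4 shows the same three-way pattern earlier: 2-hour samples on Days 8, 15 and 22 in one column, on Day 15 only in the next, and on none of these days in the third. Section 4.1 allows up to five doses over 4 weeks, which fits Days 1, 8, 15, 22 and 29.

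**Coverage by regimen after Week 5**

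- First column (weekly): 7 doses, 3 with same-visit chemistry, 7 − 3 = 4 without.
- Second column: 3 doses, 0 without.
- Third column: 1 dose, 0 without.

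**Age of the latest scheduled chemistry at each weekly dose (nominal)**

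| Dose day | Latest chemistry | Age in days |
|---|---|---|
| 36 | Day 29 | 7 |
| 43 | Day 43 | 0 |
| 50 | Day 43 | 7 |
| 57 | Day 57 | 0 |
| 64 | Day 57 | 7 |
| 71 | Day 71 | 0 |
| 78 | Day 71 | 7 |

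At the four uncovered doses the latest sample was drawn before the dose of the previous week, so no scheduled value reflects that dose.

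**Gaps between scheduled checks**

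- From Day 8 to Day 29: 7 days.
- Days 29 to 43, 43 to 57 and 57 to 71: 14 days each.
- Last on-treatment check to first follow-up, with a last dose on Day 78: 78 + 14 = 92, and 92 − 71 = 21 days. This span includes the Day 71 and Day 78 doses.

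These figures are nominal, because Table 5 allows 3 days either way on these visits.

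**Last dose day.** Tables 5 and 6 stop at Day 78. Section 4.1.1 lets Part 2b treatment run to Day 85. Footnote a of Table 5 refers to "the safety and follow-up visits on D134 and 182". The first of these days fits a Day 78 dose (78 + 56 = 134). The second does not (78 + 84 = 162), and it does not fit Day 85 either (85 + 84 = 169). If a Day 85 dose exists, it also lacks chemistry: 5 of 8 doses are uncovered, and the final gap is 85 + 14 − 71 = 28 days.

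**Exposure per weekly arm.** 6 active patients × 4 doses = 24 active doses without same-visit chemistry; 48 if both Part 2b arms are weekly; 0 if neither is.

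**With chemistry added on Days 36, 50, 64 and 78.** All 7 of 7 doses are covered, the on-treatment gap is 7 days, and the final gap is 92 − 78 = 14 days.

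**The case against.** Several points on the other side stand.

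- Section 4.1.3 is triggered by an observed rise. It does not require a result before each dose. A reader might infer that the rule has nothing to act on at the four doses; that goes too far, because a scheduled value from a week earlier exists.
- A reader might infer that dosing on Days 43, 57 and 71 waits for that day's result. Footnote d fixes only when blood is drawn, and Appendix 4 says when a local result is needed; neither makes every dose wait. For that reason the documents do not support a figure for the share of rises that would be followed by an extra dose. It would need both the turnaround of results and the timing of onset.
- The weekly regimen is an inference from redacted columns, Part 2b is optional, and a reason for two-weekly checks may sit in redacted text. The absence of a visible reason is not evidence that there is none.
- There are other protections. A weekly patient has already had five doses with chemistry at each. Part 2 doses cannot exceed the Part 1 maximum. Symptoms count in the stopping rules. An abnormal value leads to repeat testing under Section 8.2.4, so a patient already on hold would be followed and the resume step is less exposed than first detection.

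These protections do not cover one case. The repeat testing starts from an abnormal result, and further samples depend on an abnormal result, symptoms or discretion. None is a planned check for a new, silent, isolated rise, which is the pattern the protocol itself expects. Moving from weekly to two-weekly checks after five weeks can be a defensible monitoring judgement, but the public text does not present it as one, and it affects only the weekly regimen.

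**Conclusion.** The point holds as a conditional gap in the safety schedule. If Part 2b opens with a weekly arm, 4 of the 7 doses after Week 5 have no same-visit chemistry or coagulation. The latest scheduled ALT and AST at those doses are nominally 7 days old and predate the preceding dose. Gaps between checks double from 7 to 14 days, and the last is 21 days if treatment ends on Day 78.

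This rests on reading the first PK column as weekly dosing and on nominal visit days; the last dose day is uncertain in the protocol itself. The size of the clinical effect cannot be estimated from the documents. What can be said is that a silent rise may be followed by a further dose before any scheduled test could show it. The plan does not breach its own delay rule, and no statistical analysis is affected. The change is worth making because it is cheap and restores the plan's own Weeks 1 to 5 frequency for the most intensively dosed patients.

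**What to change.** In Table 5, add pre-dose blood chemistry and coagulation on Days 36, 50, 64 and 78, with a footnote limiting them to the weekly regimen. Handle them as on the other dosing days: central laboratory, with a local result under Appendix 4 if the central one will not be ready in time for dosing. State the last dose day, reconciling Section 4.1.1 and footnote a with Tables 5 and 6; if there is a Day 85 dose, add the same tests there. If two-weekly checks are intended for a weekly arm, say so in Section 4.1.3 with the reason.

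Leave the thresholds unchanged. A review-before-dose requirement on the added days alone would make them stricter than every other dosing day. Barring local results for resuming a dose would conflict with Appendix 4. Neither is needed.

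**Cost.** Eight table cells (2 rows × 4 days) and one footnote. Per weekly arm, 7 participants × 4 days = 28 extra sample sets, placebo included; 56 if both arms are weekly. Pre-dose PK blood is already drawn at these visits, so the draws themselves need no new visit. Where central results are slow, some local testing may be needed.

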4.1.4 Communication Strategy

Information will be communicated, as follows:

- The Investigator must confirm to the Sponsor that a participant has been dosed and provide a brief summary of the status of the participant in terms of safety and tolerability to RO7239958 or placebo, communicated by email or telephone.
- In Part 1, the Investigator will provide a safety assessment feedback to the Sponsor of the first two sentinel-dosed healthy participants of each cohort before proceeding to dosing the remaining participants.
- For all parts of the study and in the event of a dose-limiting adverse event (DLAE), the Investigator will contact the Sponsor immediately to discuss participant status and action taken or to be taken.
- After completion of each cohort in Part 1 (i.e., after the last participant in the cohort has reached the last day of the evaluation period, comprising 21 days of monitoring plus a further 7 days of clinical observation, for a total of 28 days), the Sponsor will organize a teleconference with the Investigators to discuss the safety and tolerability of RO7239958 or placebo, and to discuss the dose for the next cohort.

During each teleconference:

- Safety and tolerability (see [Appendix 2](#)) will be discussed along with the results of available PK data, in addition to safety laboratory results and any other available data that may assist the decision process.
- Dose escalation will only proceed if the Investigator and the Sponsor are satisfied with the safety profile of the previous cohort and agree to escalate to the next dose level.
- The decision of these meetings will be documented in writing and both the Sponsor and Investigator will approve the minutes of these meetings to confirm agreement.

For Part 2, a teleconference will be organized to discuss accumulated data from Arms 1 and 2 in Part 2a prior to the start of Arms 3 and 4; a teleconference will also be organized as above after completion of Arms 3 and 4 (*and optional Arm 5*) and before the start of subsequent arms in Part 2b if applicable.

In addition to these communications, the Sponsor and investigators will be in regular contact throughout the study by email or telephone, as per normal interactions during the conduct of a clinical study, and the Sponsor will arrange regular teleconferences and meetings to discuss study status.

4.2 SCIENTIFIC RATIONALE FOR STUDY DESIGN

The study rationale is provided in Section [2.1](#).

In order to reduce safety risks, the effects of each dose level will be reviewed carefully before escalating to the next dose level. Dose escalation will take place after a review of safety, tolerability, and available PK data, as described in Section [4.1.2](#). Stopping rules are detailed in Section [4.1.3](#). The safety observation period has been set to 21 days for the safety laboratory assessments and to 28 days for adverse event monitoring, and this approach is supported by data from the BP39405 study (RO7062931) which has completed dosing in healthy participants (see the [RO7062931 Investigator's Brochure](#)).

The DRF part of the study, Part 2a, will evaluate the safety, tolerability, PK and PD effects of multiple doses of RO7239958 in CHB patients. Part 2b is an extension part of Part 2a to evaluate alternative regimens, additional safety, PK and PD data, if required.

[REDACTED] The approach is based on the consideration that the PK profile of RO7239958 is anticipated to show minimal variation between healthy participants and patients, and that the doses in Part 2 will never exceed the maximum safe dose defined in healthy volunteers in Part 1. Opening Part 2a with two parallel dosing levels will increase the likelihood of detecting antiviral activity and identifying a dose for regimen optimization in subsequent arms, while remaining within acceptable safety margins, based upon non-clinical data and data from Part 1.

In this study RO7239958 will be given as an add-on to NUC treatment. It is envisaged that in future studies RO7239958 will contribute to combination regimens with one or more antiviral agents or immune-enhancers, with the aim of inducing a HBV cure.

